2 STUDY OBJECTIVES AND ENDPOINTS

2.1 Objectives

2.1.1 Primary Objectives

The following are the primary objectives for Phase 1 and Phase 2:

Phase 1

- To determine the safety and tolerability, MTD or maximum administered dose (MAD), and RP2D of the combination of rociletinib and MPDL3280A;
- To assess the PK profile of rociletinib (and its metabolites) and MPDL3280A when given in combination.

Phase 2

- To determine the efficacy of the combination of rociletinib and MPDL3280A based on overall response rate per RECIST v1.1 (Appendix A) in the following groups of patients:
 - **Group A**: Patients with EGFRm advanced or metastatic NSCLC who have not previously received an EGFR TKI or chemotherapy.
 - **Group B:** Patients with EGFRm advanced or metastatic NSCLC who have progressed on a prior EGFR TKI.

2.1.2 Secondary Objectives

The following are the secondary objectives for Phase 1 and Phase 2:

Phase 1

• To determine preliminary efficacy and pharmacodynamics of the combination of rociletinib and MPDL3280A in enrolled patients.

Phase 2

- To determine the efficacy of the combination of rociletinib and MPDL3280A based on ORR per modified RECIST incorporating immune related response criteria (irRC; Appendix B) in Groups A and B;
- To assess the activity of the combination of rociletinib and MPDL3280A based upon DOR and PFS;
- To assess the pharmacodynamic relationship between biomarkers and clinical activity, and/or resistance to study drug.

2.2 Endpoints

2.2.1 Primary Endpoints

The following are the primary endpoints for Phase 1 and Phase 2:

Phase 1

- Treatment-emergent AEs;
- DLTs;
- PK parameters for rociletinib (and its metabolites) and MPDL3280A.

Phase 2

• ORR according to RECIST v1.1 (Appendix A) as determined by Investigator assessment.

2.2.2 Secondary Endpoints

The following are the secondary endpoints for this study:

- ORR according to modified RECIST incorporating irRC (Appendix B);
- Duration of response, DCR, and PFS according to RECIST v1.1 (Appendix A) as determined by Investigator assessment;
- Duration of response, DCR, and PFS according to modified RECIST incorporating irRC (Appendix B);
- Overall survival (OS);
- Change from baseline in mutant EGFR levels in circulating tumor DNA (ctDNA) obtained from plasma.

2.2.3 Exploratory Endpoints

The following are the exploratory endpoints for this study:

- Positive and negative percent agreement between blood and tissue results for T790M and EGFR activating mutations;
- Incidence of ATA response to MPDL3280A and potential correlation with PK, pharmacodynamics, safety and efficacy parameters;
- Identification of biomarkers associated with response or resistance to rociletinib and/or MPDL3280A;
- Changes in expression of immune-related markers (including but not limited to granzyme B or other exploratory markers) in archival and/or fresh tumor tissue prior to and after MPDL3280A and rociletinib treatment;
- Markers of RAS-RAF-MEK signaling cascade (including but not limited to EGFR) in archival and/or fresh tissue;
- PD-L1 status by immunohistochemistry (IHC) or quantitative polymerase chain reaction (PCR) in archival and/or fresh tissue.

Clovis Oncology, Inc. Rociletinib (CO-1686) FINAL Version 1.0

3 STUDY DESIGN

This is a multicenter, open-label, non-randomized study in patients with EGFRm advanced or metastatic NSCLC to be conducted in two phases: a Dose Finding Phase (Phase 1) and a Dose Expansion Phase (Phase 2). A schematic of the study design is presented in Figure 1.

BID, twice daily; DOR, duration of response; EGFRm, epidermal growth factor receptor mutatant; MAD, maximum administered dose; MTD, maximum tolerated dose; NSCLC, non-small cell lung cancer; ORR, overall response rate; PFS, progression-free survival; T790M–, T790M mutation-negative; T790M+, T790M mutation-positive; TKI, tyrosine kinase inhibitor; TPI, toxicity probability interval.

3.1 Clinical Safety Committee

Throughout the study, oversight will be provided by the Clinical Safety Committee (CSC), comprised of all Principal Investigators, the Sponsor's Medical Monitor and the Sponsor's drug safety representative. The CSC will:

- Review and confirm all DLTs;
- Determine all cohort dose-escalation and de-escalation decisions (assignment of Dosing Cohorts) during the Dose Finding Phase (Phase 1);
- Determine the MAD or MTD and RP2D to extend into the Expansion Phase (Phase 2), based on available safety, tolerability, and PK data;
- Review safety data for all patients during Phase 1 and Phase 2.

3.2 Dose Finding Phase (Phase 1)

The Dose Finding Phase will be conducted with patients who have progressed after at least 12 weeks of treatment with a prior first- or second-generation EGFR TKI (ie, erlotinib, gefitinib, afatanib), regardless of T790M mutation status. The Dose Finding Phase will be used to determine the MTD or MAD and RP2D of the combination of rociletinib and MPDL3280A, and to evaluate the safety, tolerability, and PK profile of the combination treatment. The Dose Finding Phase will include a 7-day Run-in-Period of rociletinib monotherapy prior to the initiation of combination treatment. Patients will receive daily oral BID doses of rociletinib at the Dosing Cohort-defined dose level (Section 3.2.2). Patients who experience an AE that requires a reduction or more than 48-hour delay in dose of rociletinib during the Run-in-Period will not go on to receive the combination of rociletinib and MPDL3280A, but will remain on study to receive rociletinib monotherapy; an additional patient will be enrolled as a replacement for inclusion in the same Dosing Cohort.

For the Dose Finding Phase, Cycle 1 will begin with the initiation of combination treatment following a successful completion of the Run-in-Period and will be used for the determination of DLTs. Patients will continue to receive daily oral BID doses of rociletinib (at the Dosing Cohort-defined dose level) and IV doses of MPDL3280A on Day 1 of each cycle, in consecutive 21-day cycles. Thereafter, treatment and monitoring of patients will be conducted in 21-day treatment cycles. Patients will be evaluated regularly for safety, PK, efficacy and pharmacodynamics according to the Schedule of Assessments (see Table 1). For further details on the planned assessments and analyses of safety, PK, efficacy and pharmacodynamics, please refer to Sections 8.4.2-8.4.5.

3.2.1 Dose-Limiting Toxicity

Determination of DLTs will be made during the first 21 days of combination treatment with rociletinib and MPDL3280A (ie, during Cycle 1 after the rociletinib Run-in-Period) in the Dose Finding Phase. A DLT is defined as a clinically significant AE or laboratory abnormality assessed as at least related to the study drug (rociletinib and/or MPDL3280A), unrelated to disease progression, and that meets any of the following criteria:

Cytopenia:

- Grade 4 neutropenia persisting for more than 7 days;
- Febrile neutropenia, defined as an absolute neutrophil count (ANC) < 1000/mm³ and a single temperature of > 38.3°C (101°F);
- Grade 4 thrombocytopenia persisting for more than 7 days or thrombocytopenia with clinically significant bleeding (ie, bleeding that requires blood or platelet transfusion or other medical intervention, or that may cause disability or death, such as cerebral hemorrhage).

Organ Toxicity:

• Grade \geq 3 symptomatic hepatic toxicities lasting for > 48 hours, or Grade \geq 3 asymptomatic hepatic toxicities lasting for > 7 days with the following exception:

- For patients with Grade 2 Alkaline phosphatase (ALP) abnormality at baseline, an increase to > 8 × the upper limit of normal (ULN) lasting > 48 hours (if symptomatic) or > 7 days (if asymptomatic) will be considered a DLT.
- Grade \geq 3 nonhematologic, nonhepatic organ toxicity, with the following exceptions:
 - **DLT Toxicity Exceptions**
 - Grade 3 nausea, vomiting, or diarrhea that resolves to Grade ≤ 1 within 7 days after starting appropriate supportive therapy (see Section 6.2.2);
 - Grade ≥ 3 asymptomatic or mildly symptomatic rash that can be adequately managed with supportive care (see Section 6.2.4) or symptomatic rash that resolves to become asymptomatic and/or Grade ≤ 2 within 7 days of appropriate supportive therapy;
 - Grade \geq 3 fatigue that resolves to Grade \leq 2 within 7 days;
 - Grade 3 arthralgia that can be adequately managed with supportive care or that resolves to Grade ≤ 2 within 7 days;
 - Grade 3 autoimmune thyroiditis or other endocrine abnormality that can be managed by endocrine therapy and that would not necessitate initiation of systemic corticosteroids;
 - Grade 3 fever (in the absence of any clinically significant source of fever) that resolves to Grade ≤ 2 within 7 days with supportive care;
 - Grade 3 laboratory abnormality that is asymptomatic and deemed by the Investigator to be not clinically significant;
 - Grade ≥ 3 hyperglycemia lasting ≤ 7 days. Grade > 3 hyperglycemia will be considered a DLT only if it lasts for more than 7 days despite optimized antihyperglycemic treatment (eg, oral anti-hyperglycemic therapy);
 - Grade ≥ 3 elevation of serum creatine kinase (CK) level that is asymptomatic (ie, not accompanied by signs, symptoms, or other laboratory abnormalities associated with rhabdomyolysis or myocardial injury) that is deemed by the Investigator to be clinically insignificant and that returns to Grade ≤ 2 within 7 days.

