namics	A mandatory fresh tumor tissue biopsy specimen will be collected within 60 days prior to the first day of study treatment for all patients. In addition, an optional fresh tumor biopsy may be collected at time of permanent treatment discontinuation due to disease progression (at the time the Investigator believes the patient is no longer deriving clinical benefit from study treatment, if treatment beyond radiographic disease progression is approved). The baseline tissue biopsy specimen from screening will be used for a retrospective confirmation of EGFR mutation status by a central laboratory. The baseline biopsy as well as the optional tissue biopsy collected at progression will also be used to investigate mechanisms of response, primary resistance, and acquired resistance to rociletinib and MPDL3280A. Blood samples will be collected for pharmacogenomic and pharmacodynamics analyses. The pharmacogenomic blood sample will be collected predose on C1D1 for genomic deoxyribonucleic acid (DNA) purification. The DNA sample may be evaluated by next generation sequencing (NGS), and molecular alterations in germline and tumor DNA may be compared so that molecular alterations unique to the tumor that may modulate response or resistance to EGFR targeted therapy can be unambiguously identified. Pharmacodynamic blood samples will be collected and processed as described in Table 2 and Section 8.4.5.
Statistical Procedures	Statistical methods are described in Section 10.

THIS PAGE IS INTENTIONALLY LEFT BLANK

Table 1: Study CO-1686-032 Schedule of Assessments

				Trea	tment Period			
	Screening Period	Rociletinib 7-day Run- In- Period (Phase 1 only)	Cycle 1 combination therapy (21-day cycle) Cycle 2+ combination therapy (21-day cycle)			End of Treatment ^C	Follow Up	
Procedure ^A	Day -28 to Day 0	Day 1 ^B	Day 1 ^B	Day 4	Days 8 and 15 ±2 days	Day 1 ±3 days		
Informed consent	Х							
Documentation of EGFR mutational status ^D	Х							
Medical/oncology history ^E	Х							
Physical examination	Complete ^{F,G}	Limited ^H	Complete ^G	Limited ^H	Limited ^H	Limited ^H	Complete ^G	
ECOG performance status ^I	X ^F	Х	Х			Х	Х	
Vital signs ^J	\mathbf{X}^{F}	X	Х	Х	X	Х	Х	
Hematology (including reticulocytes) ^K	X ^F	Х	X		X	Х	X	
Coagulation tests ^L	\mathbf{X}^{F}							
Urinalysis ^M	Х							
Fasting_serum chemistry ^N	X ^F	Х	Х			Х	Х	
Fasting blood glucose ⁰				Х	X			
Serum pregnancy test ^P	Х						Х	
Hemoglobin A1c	Х					Odd cycles		
TSH, free T_3 and free T_4^Q	Х					Х	Х	

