At each dose level, after the first evaluable 3 patients have completed Cycle 1, the CSC will meet to evaluate the Dosing Cohort data and to make a decision on the next step for Dosing Cohort assignment (increase dose, decrease dose, maintain same dose, or stop), which will be guided by the mTPI decision table (Appendix H). A patient will be deemed evaluable for safety and DLT determination if they have received at least 75% of the planned total dose of each drug within Cycle 1. Patients who receive <75% of the planned total dose of either rociletinib or MPDL3280A for reasons other than study drug-related AEs will not be included in the evaluation of the Dosing Cohort and will be replaced. If the dose is maintained, up to an additional 6 patients may be enrolled at the same dose, and the next safety evaluation will take place after all patients have completed Cycle 1. The CSC may decide to meet at any time to evaluate a Dosing Cohort if a safety signal arises or other data become available to justify re-evaluation of the Dosing Cohort before it is fully enrolled.

The enrollment/evaluation process will continue until at least 6 patients have been treated at any single dose level or enrollment of the maximum sample size of 18 patients for the Phase 1 portion of this study has been achieved.

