3.4 Study Conduct and Duration of Patient Follow-Up

The study will comprise a Screening Period, and Treatment Period, and a Follow-up Period as outlined in Table 6. Please refer to Section 8 for additional details.

	Sign ICF						
COFFNINC DEDIOD	Screening Assessments						
SCREENING PERIOD	Up to 28 days before 1st dose of study drug (biops	sy within 60 days pi	rior)				
	Enrollment						
	Study assessments every 21 days. Additional ECG and glucose		Day 1				
TREATMENT PERIOD	monitoring during Cycle 1 (Day 4, Day 8, and Day 15). Tumor	Cycle 1	Day 4				
Oral rociletinib BID + IV	assessments every 2 cycles through Cycle 6 (end of Cycles 2, 4, and 6): every 3 cycles after Cycle 6 (end of Cycles 9, 12, etc.); and	Cycle I	Day 8				
MPDL3280A every 21days	at the EOT Visit. The frequency of tumor assessments may be		Day15				
	reduced after 2 years with approval of Medical Monitor.	Cycle 2 +	Day 1				
		Ļ					
	Disease Progression	Rociletinib and	/or MPDL3280A				
		treatment post-progression (Spons					
	(Optional post-progression tumor biopsy)	approval) with con	rotocol				
		↓ .					
	Treatment discontinuation						
END OF STUDY PERIOD	Follow-up Safety Assessment						
	28 days after last dose of study drug (rociletinib or MPDL3280A)						
	PK/ATA blood samples 120 days after last dose of MPDL3280A (see Table 2)						
	Follow-up for subsequent anticancer therap	vies and survival					
	Every 12 weeks						

Table 6:Study Schematic (CO-1686-032)

ATA, anti-therapeutic antibody; BID, twice-daily; ICF, informed consent form; IV, intravenous; PK, pharmacokinetics

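### The Cycle 1 schedule has no liver test between C1D1 and C2D1, so a new asymptomatic hepatic DLT can go undetected; how often is unknown

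*Combined protocol and SAP*

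**What the plan says.** Section 3.2.1 fixes the window: "Determination of DLTs will be made during the first 21 days of combination treatment with rociletinib and MPDL3280A". A DLT must be clinically significant, related to study drug and not due to progression. One criterion is Grade 3 or higher "asymptomatic hepatic toxicities lasting for > 7 days with the following exception". The exception covers patients with Grade 2 alkaline phosphatase at baseline, who need a rise above 8 × ULN, again for more than 7 days if asymptomatic.

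ALT, AST, alkaline phosphatase and bilirubin belong to the serum chemistry panel (Table 1 footnote N; Section 8.4.2.2). In Table 1 the row "Fasting_serum chemistry" is marked at screening, Run-in Day 1, C1D1, Day 1 of Cycle 2 onward and end of treatment. It is blank at C1 Days 4, 8 and 15. Two other places agree. Table 6 reads "Study assessments every 21 days. Additional ECG and glucose" for the mid-cycle visits and adds no liver tests, and Table 13 describes standard liver monitoring as three-weekly, before dosing.

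Other criteria with a 7-day duration are sampled in mid-cycle. Hematology is drawn on Days 8 and 15, which serves "Grade 4 neutropenia persisting for more than 7 days". Fasting glucose is drawn on Days 4, 8 and 15, which serves the rule that "hyperglycemia will be considered a DLT only if it lasts for more than 7 days".

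On the cohort decision, Section 3.2.2 says that "after the first evaluable 3 patients have completed Cycle 1, the CSC will meet to evaluate the Dosing Cohort data", guided by the Appendix H table.

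**The concern.** DLTs are a Phase 1 primary endpoint and the only input to the Appendix H table. A DLT criterion should be measurable on the protocol's own schedule. Here, an asymptomatic patient whose C1D1 liver tests are unremarkable need not be tested again until the DLT window is closing or closed. An event that meets the criterion can begin and end in between. If it is still present at C2D1, a single raised value does not date its onset, and the protocol does not say whether it counts toward Cycle 1 when the Clinical Safety Committee (CSC) meets.

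The error runs one way: a missed event can only lower the count. Section 6.2.3 links immune-mediated hepatitis to MPDL3280A, and the dose selected in Phase 1 goes forward to up to 75 Phase 2 patients.

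**Working it through.** The plan gives no figure on this point to reproduce. The checks are the timing, the effect of a miss on Appendix H, and what the documents say about the hepatic rate.

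**1. Timing.** Inputs: window Days 1 to 21 (Section 3.2.1); scheduled liver tests at Day 1 and at Day 22 ± 3 (Table 1, Section 8).
- Take an event with onset on Day o that is present through Day o + d − 1 and resolved on Day o + d, so that it lasts d elapsed days.
- More than 7 days means d ≥ 8, and reaching that by Day 21 needs o + 8 ≤ 21, so o ≤ 13. New onset after the C1D1 test gives o = 2 to 13, which is 12 onset days. They are assumed equally likely.
- A test on Day t sees the event if o ≤ t ≤ o + d − 1.

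| Duration d | Seen at C2D1, Day 22 | Seen at Day 8 or 15, if drawn |
|---|---|---|
| 8 days | 0/12 (needs o ≥ 15) | 12/12 |
| 10 days | 1/12 (needs o ≥ 13) | 12/12 |
| 14 days | 5/12 (needs o ≥ 9) | 12/12 |
| 21 days | 12/12 (needs o ≥ 2) | 12/12 |

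Visit windows change this somewhat. For an 8-day event, a C2D1 test as early as Day 19 sees 2/12 (o = 12 and 13). Added draws taken on Days 6 and 17, within the ± 2-day window, would miss o = 7, 8 and 9 and so see 9/12. If both end days are counted, the latest onset becomes Day 14 and the Day 22 column becomes 0/13, 2/13, 6/13 and 13/13. The conclusion is the same.

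**2. Effect of one miss.** With a Beta(1,1) prior, target 33%, interval 28% to 38% and the 95% exclusion rule, the Appendix H cells for 3 and 6 patients are reproduced. One missed DLT turns 2/3 (D) into 1/3 (S), and 4/6 (DU) into 3/6 (S).

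**3. Illustration.** Assume other DLTs occur at 20% and hepatic DLTs of this type at rate h, independently. With full ascertainment p = 1 − (1 − 0.20)(1 − h). If every hepatic event is missed, p = 0.20, which is the upper bound on the effect. P(D or DU) is P(X ≥ 4) for n = 6 and P(X ≥ 2) for n = 3, with X binomial.

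| | p | n = 6 | n = 3 (interim) |
|---|---|---|---|
| All hepatic events missed | 0.200 | 1.7% | 10.4% |
| None missed, h = 1% | 0.208 | 2.0% | 11.2% |
| None missed, h = 5% | 0.240 | 3.3% | 14.5% |
| None missed, h = 10% | 0.280 | 5.6% | 19.1% |

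The n = 3 column is interim because Section 3.2.2 continues enrollment to at least 6 patients at one dose, or 18 in total.

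**4. Hepatic rate.** The documents give none for the combination. For rociletinib alone, Table 3 shows one related transaminase SAE in 148 patients (0.7%, exact 95% CI 0.02% to 3.7%) and none in the 18 + 17 + 50 + 6 = 91 on the HBr salt (upper 95% limit 4.0%). Table 4 lists no hepatic term at 5% or more. Section 1.4.1 reports no DLT for MPDL3280A, though it does mention hepatitis and raised liver tests. SAE counts do not measure asymptomatic Grade 3 values, so none of these figures bounds h.

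**The case against.** The strongest reply is that the protocol has other routes to a liver test and other safeguards on the dose decision.

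- **Other tests.** Section 6.2.3 requires immediate liver tests for suggestive symptoms, Table 13 requires at least weekly tests above 3 × ULN, and Section 8.4.2.2 allows discretionary tests. None of these is required for an asymptomatic patient with unremarkable C1D1 values, so the detection gap remains.
- **Follow-up after detection.** This part stands. Table 13 has tests every 48 to 72 hours at the higher thresholds, and Table 18 has every-other-day tests for related asymptomatic Grade 3 or higher AST, ALT or bilirubin attributed to both agents. Duration can be documented once an event is found.
- **Comparison with other criteria.** A reader might infer that hematology and glucose draws on Days 8 and 15 settle their 7-day rules. They do not: those draws are nominally exactly 7 days apart. Their advantage is earlier detection.
- **Clinical significance.** Not every transient elevation would be a DLT, because the general definition requires clinical significance. That can be judged only on a value that was measured. The listed exception for asymptomatic, insignificant Grade 3 laboratory values applies to nonhepatic toxicity.
- **Safeguards.** The run-in means that C1D1 chemistry follows 7 days of rociletinib alone. The CSC may meet at any time and sets the Phase 2 dose on cumulative data, Section 5.7.4 covers later DLT-equivalent toxicity, and Table 5 plans no dose above 500 mg BID. These limit the consequence.

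It is also fair that Tables 1, 6 and 13 agree on three-weekly testing. They do not contradict one another; the mismatch is between that schedule and the duration-based DLT criterion.

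**Conclusion.** The point holds as a gap in first detection and is worth fixing because the remedy is cheap. Between the first combination dose and Day 19 there is no scheduled liver test. A qualifying 8-day asymptomatic event with new onset is never seen at a nominal C2D1, and a 14-day event is seen for 5 of 12 onset days, assuming uniform onset on Days 2 to 13.

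A reader might infer that the recommended Phase 2 dose will be set too high, or that hepatic DLTs cannot be recorded at all. The documents support neither. Symptomatic events, already abnormal patients and discretionary tests all have a route to detection, and the hepatic rate is unknown. With other DLTs assumed at 20% and every hepatic event missed, the chance of a D or DU cell at six patients falls from 2.0% to 1.7% at an assumed 1% hepatic rate, and from 3.3% to 1.7% at 5%. The direction is certain; the size is not, and it may be small.

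**What to change.** Reconcile the hepatic criterion in Section 3.2.1 with the Cycle 1 schedule in Tables 1, 6 and 13, so that the criterion can be measured.

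1. For Phase 1 only, add the liver tests to the existing C1D8 and C1D15 blood draws.
2. In Section 3.2.1, define how duration is counted (elapsed days or both end days included) and say that it is established from the repeat tests already in Tables 13 and 18. Two draws 7 days apart cannot show more than 7 days by themselves. The triggers in those tables are AST, ALT and bilirubin, so name the tests that serve the alkaline phosphatase criterion.
3. State how an elevation first seen at C2D1, or unresolved at Day 21, is counted before the CSC applies Appendix H.

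Cost: 2 × 18 = 36 panels, plus 2 per replaced patient, and up to 2 × 6 = 12 more if the optional safety expansion cohort is additional to the 18. No new visit is needed. The downside is that more elevations will be found and will trigger the existing follow-up provisions. No change to patient management is proposed.

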1.4.1 Safety of MPDL3280A from Clinical Studies

The presented safety data for MPDL3280A have been derived from the treatment of patients in Study PCD4989g. In this study, patients are receiving MPDL3280A monotherapy. No DLTs have been observed at any dose level and no MTD was established.

As of 10 May 2014, in the PCD4989g study, 412 patients have been treated with MPDL3280A. The PCD4989g study consisted of patients with NSCLC, renal cell carcinoma, melanoma, and urothelial bladder cancer (88, 69, 45, and 79 patients, respectively), as well as other tumor types.

The majority of AEs reported were Grade 1 or 2 in maximum severity (based on National Cancer Institute Common Terminology Criteria for Adverse Events Version 4.03 [NCI CTCAE v4.03].²⁴ The most frequently observed AEs (occurring in $\geq 10\%$ of treated patients) included fatigue, nausea, decreased appetite, pyrexia, dyspnea, diarrhea, constipation, cough, headache, back pain, vomiting, anemia, arthralgia, rash, insomnia, asthenia, abdominal pain, chills, and pruritus.

Given the mechanism of action of MPDL3280A, events associated with inflammation and/or immune-mediated AEs are being closely monitored during the MPDL3280A clinical program. Potential immune-related events that have been reported include dermatologic, hepatic, endocrine, and respiratory events (eg, pneumonitis); hepatitis/elevated liver function tests (LFTs); and influenza-like illness.

Dyspnea, cough, fatigue, hypoxia, pneumonitis and pulmonary infiltrates have been associated with the administration of MPDL3280A and have primarily been observed in patients with underlying NSCLC. Mild to moderate events of pneumonitis have been reported with MPDL3280A.

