5.7.2 Phase 1 – Run-in-Period

Rociletinib monotherapy will be administered orally BID during the 7-day Run-in-Period. Dose reductions of rociletinib during the Run-in-Period are not allowed for reasons other than a DLT. Dose delays of rociletinib for up to 48 hours for toxicity management is allowed. Any patient who experiences an AE(s) that requires either a delay of treatment for more than a total of 48 hours or a dose reduction during the 7-day Run-in Period of rociletinib monotherapy will not be eligible for combination therapy. Such a patient will only receive monotherapy rociletinib for the duration of participation in the study.

5.7.3 Phase 1 – Cycle 1

The first dose of MPDL3280A at 1200 mg will be administered by IV on C1D1. Dose reductions of rociletinib are not allowed for reasons other than a DLT or a decision by the CSC based on emerging safety data. Dose delays of rociletinib are not allowed for reasons other than toxicity. Patients are eligible for safety and DLT evaluation of the cohort if they receive at least 75% of the planned total dose of each study drug within Cycle 1 or they experience a DLT at any time during Cycle 1.

5.7.4 Beyond DLT Assessment (Phase 1 – Cycle 2+ and Phase 2 – All Cycles)

For patients who experience a toxicity that is equivalent to a DLT – If the toxicity is assessed as being related to rociletinib, the next dose of rociletinib should be held until resolution of the toxicity to Grade 1 or to the baseline level (if severity > Grade 1 at baseline) and then reduced to the next dose level of rociletinib (Table 7), unless permanent discontinuation of rociletinib is required per toxicity management guidelines of the protocol (Sections 6.1 and 6.3). If the toxicity is assessed as being related to MPDL3280A, the next dose of MPDL3280A should be held until the toxicity has resolved to Grade 1 or to the baseline level (if severity > Grade 1 at baseline), unless permanent discontinuation of MPDL3280A is required per toxicity management guidelines of the protocol (Sections 6.2 and 6.3). In addition, because there is no available antidote for MPDL3280A and discontinuation of MPDL3280A may not have immediate therapeutic effect, consideration may be given to holding rociletinib doses temporarily even if the toxicity is not attributed to rociletinib.

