	 Begin/continue maximum supportive care and adequate combination anti-emetic treatments (see Section 7.6.1 for guidance on avoiding QT-prolonging concomitant medication). Consider gastroenterology consult;
	 Hold both rociletinib and MPDL3280A until < Grade 1. Restart rociletinib at next lower dose. If no recurrent symptoms, restart MPDL3280A;
	• If Grade \geq 3 nausea/vomiting recurs, MPDL3280A should be discontinued.

Toxicity	Attribution to both agents
Ocular Toxicity:	Grade ≥ 2:
	 Hold both study drugs until < Grade 1 (dose delays longer than 14 days require discussion with the Medical Monitor);
	 Obtain ophthalmology consult; uveitis or episcleritis may be treated with topical corticosteroid eye drops;
	 Reintroduce rociletinib at a reduced dose when symptoms resolved to Grade ≤ 1. If no recurrent symptoms, restart MPDL3280A; MPDL3280A should be permanently discontinued for immune-mediated ocular disease that is unresponsive to local immunosuppressive therapy.
Laboratory abnormalities	Grade \geq 3 Laboratory abnormalities related to study drug that are asymptomatic and deemed by the Investigator not to be clinically significant
	 After discussion between Investigator and Medical Monitor, rociletinib dosing may be delayed, and treatment subsequently resumed at the current dose level or at a reduced dose. If abnormality persists > 7 days, MPDL3280A dosing may also be held and subsequently resumed at the same dose level when toxicity resolves to baseline grade plus one.
Liver toxicities	Grade \geq 3 AST, ALT, or bilirubin abnormalities (or AST or ALT \geq 10 × ULN in patients with hepatic metastases) related to study drug that are asymptomatic and deemed by the Investigator not to be clinically significant
	• Hold both study drugs until recovery Grade ≤ 1 ;
	 Initiate systemic steroids IV for 48 hours followed by oral taper;
	 Monitor LFTs QOD until decreasing, then weekly;
	 If resolved to baseline grade plus one (eg, if baseline Grade 1, then Grade 2) resume MPDL3280A dosing;
	 If AE persists permanently discontinue MPDL3280A.
Other Grade ≥ 3 non-hematologic or Grade 4	 Hold rociletinib and MPDL3280A until recovery to Grade ≤ 1 and then restart rociletinib at a reduced dose and MPDL3280A at the same dose.
hematologic toxicity	 If the Grade 4 AE recurs (a second time), then MPDL3280A should be discontinued.
	 If the Grade 4 AE recurs (a third time), then rociletinib should be discontinued.

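### Isolated drug-related anemia, even Grade 4 or fatal, meets no DLT criterion in Section 3.2.1, so it would not enter the mTPI count

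*Combined protocol and SAP*

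**What the plan says.** Section 3.2.1 requires a DLT to be clinically significant, drug-related, "unrelated to disease progression, and that meets any of the following criteria". The criteria that follow are:

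- **Cytopenia:** "Grade 4 neutropenia persisting for more than 7 days"; febrile neutropenia; and "Grade 4 thrombocytopenia persisting for more than 7 days or thrombocytopenia with clinically significant bleeding".
- **Hepatic:** Grade ≥3 hepatic toxicity beyond stated durations.
- **General:** Grade ≥3 "nonhematologic, nonhepatic organ toxicity, with the following exceptions", followed by the exceptions.

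There is no hemoglobin criterion, no general Grade 4 hematologic criterion and no criterion for drug-related death. Section 8.4.2.2 places hemoglobin in the hematology panel, and inclusion criterion 4 lists it under bone marrow function. By the protocol's own classification, anemia is therefore hematologic.

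Three other places bear on this:

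- Table 18 (Section 6.3), under the column for toxicity attributed to both agents, has a row beginning "Other Grade ≥ 3 non-hematologic or Grade 4" and continuing to hematologic toxicity. It holds both drugs until recovery to Grade ≤1, then restarts rociletinib at a reduced dose.
- Section 5.7.3 and Table 8 do not allow a Phase 1 Cycle 1 rociletinib reduction except for a DLT or by CSC decision.
- Section 1.4.1 names anemia among the adverse events seen in at least 10% of MPDL3280A patients: "headache, back pain, vomiting, anemia, arthralgia, rash, insomnia, asthenia, abdominal pain, chills, and pruritus".

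**The concern.** The mTPI decision table has one toxicity input, the number of DLTs among the patients treated at the current dose. The MTD is the dose whose estimated toxicity is closest to 33%. With 3 to 9 patients at a dose (3, then up to 6 more under Section 3.2.2), a single event can move the decision.

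If a severe hematologic event caused by the drugs cannot be entered as a DLT, the table returns the recommendation for one fewer toxicity and the estimated rate is biased downward.

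The omission also leaves Phase 1 Cycle 1 with conflicting instructions. Table 18 calls for a reduced rociletinib dose on restart. The Cycle 1 rule forbids that reduction because the event is not a DLT, unless the CSC decides otherwise.

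**Working it through.** **1. Does any criterion capture isolated anemia?** Take a drug-related Grade 4 anemia in Cycle 1 with normal neutrophils and platelets.

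| Section 3.2.1 item | Met? |
|---|---|
| Prolonged Grade 4 neutropenia; febrile neutropenia | No |
| Thrombocytopenia, prolonged Grade 4 or with bleeding | No |
| Hepatic toxicity | No |
| Grade ≥3 nonhematologic, nonhepatic toxicity | No, the event is hematologic |

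The result is the same if the anemia is fatal. Two routes into the count remain: bleeding with thrombocytopenia, or a consequence separately reported as a Grade ≥3 nonhematologic event.

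**2. Reproduce the plan's table.** Inputs from Appendix H are a target of 33%, an equivalence interval of 28% to 38%, and exclusion (U) if P(p > 0.33) > 0.95. A Beta(1,1) prior is assumed because none is stated. With x DLTs in n patients the posterior is Beta(1+x, 1+n−x). Each decision is scored by posterior probability divided by interval width (0.28, 0.10 and 0.62), and the largest score wins. All 91 cells checked (0 to 7 DLTs, n up to 14) match the printed table; rows 8 to 14 were not checked. The cells used here are:

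| DLTs/n | E | S | D | P(p > 0.33) | Decision |
|---|---|---|---|---|---|
| 1/3 | 1.119 | 1.768 | 0.823 | 0.599 | S |
| 2/3 | 0.248 | 0.876 | 1.360 | 0.892 | D |
| 3/3 | 0.022 | 0.147 | 1.579 | 0.988 | DU |
| 3/6 | 0.363 | 1.505 | 1.206 | 0.832 | S |
| 4/6 | 0.076 | 0.569 | 1.487 | 0.957 | DU |

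**3. Remove one event from the count.**

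| True count | Count as recorded | Decision due | Decision given |
|---|---|---|---|
| 1/3 | 0/3 | S | E |
| 2/3 | 1/3 | D | S |
| 3/3 | 2/3 | DU | D |
| 1/6 | 0/6 | E | E |
| 2/6 | 1/6 | S | E |
| 3/6 | 2/6 | S | S |
| 4/6 | 3/6 | DU | S |

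At Cohort 1 (500 mg BID) the E-versus-S rows matter only if the CSC opens a higher dose, because Table 5 plans none. Cohort −1 is the lower fallback dose; an E there would point back to 500 mg BID, and the point does not rest on that case.

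**4. Effect on the estimate.** The observed rate falls by 1/n: 2/3 (67%) becomes 1/3 (33%), which is the target itself; 4/6 (67%) becomes 3/6 (50%).

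**5. Evaluability.** Scoring the patient as a non-DLT is exact only with at least 75% of the planned dose of each drug. For rociletinib, 25% of 21 days is 5.25 days, so a longer hold takes the patient below the limit. Section 5.7.3 then makes the patient evaluable only with a DLT. Section 3.2.2 excludes and replaces only patients who fall short for reasons other than drug-related events. The patient may count as a non-DLT or leave the denominator; either way the event is not counted.

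**The case against.** The strongest reply is that the count does not decide alone. Section 3.2.2 says that mTPI guides decisions. Under Section 3.1 the CSC makes every cohort decision and sets the RP2D on safety, tolerability and PK data. It may meet at any time on a safety signal. A reader might infer that a fatal anemia would pass as a success; the documents do not support that. What remains is that the CSC's stated role on DLTs is to review and confirm them, and no text lets it add an unlisted event to the count.

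Other stronger readings also fail:

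- **Table 18 as proof that the DLT list is wrong.** That row governs management, applies to toxicity attributed to both agents, and already differs from the DLT list: Grade 4 neutropenia, or Grade 4 thrombocytopenia without significant bleeding, lasting 7 days or less falls in the row but is not a DLT. What stands is the conflict with the Cycle 1 reduction rule.
- **Carry-over into later cycles and Phase 2.** Section 5.7.4 does begin "For patients who experience a toxicity that is equivalent to a DLT", but Table 8 allows Cycle 2+ holds and rociletinib reductions for toxicity, and Table 18 has no cycle limit. Management is not missing there.
- **A likely frequency.** Assuming a 2% to 5% event rate would give 1 − 0.98^6 = 11.4% to 1 − 0.95^6 = 26.5% for at least one event in six patients, but no document supports that rate. Table 3 shows no treatment-related anemia SAE among 148 rociletinib patients (one-sided 95% upper bound 1 − 0.05^(1/148) = 2.0%, monotherapy, not limited to Cycle 1). The anemia entry in Section 1.4.1 is neither graded nor attributed, and no DLTs were seen with MPDL3280A alone.

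The omission may be deliberate, since entry allows hemoglobin of 9 g/dL reached by transfusion. The documents do not say so.

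**Conclusion.** The concern holds in this limited form. Followed as written, Section 3.2.1 keeps an isolated drug-related anemia of any grade out of the DLT count, and the mTPI input and toxicity estimate are then one event too low. The consequential changes at the planned starting dose are D to S (2/3 read as 1/3), DU to D (3/3 read as 2/3) and DU to S (4/6 read as 3/6). Each needs at least one other DLT already counted; the last needs three. At n = 6, moving from 0 to 1 or from 2 to 3 changes nothing.

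The conclusion rests on reading the list as closed and on the protocol's own placing of hemoglobin under hematology. The reproduction of the table also rests on the assumed Beta(1,1) prior. How often the gap would matter cannot be estimated from the documents. CSC oversight lessens the risk of a wrong dose decision but does not correct the count.

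**What to change.** Reconcile Section 3.2.1 with the Table 18 row on other Grade 4 hematologic toxicity and with the Cycle 1 reduction rule in Section 5.7.3 and Table 8. The DLT definition should state how drug-related hematologic events other than neutropenia and thrombocytopenia, and drug-related deaths, enter the DLT count. The threshold is for the sponsor to set. If the exclusion is intended, the protocol should say so and give the reason. In the same edit, align the evaluability wording of Sections 3.2.2 and 5.7.3 for patients who fall below 75% dosing because of a drug-related event.

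The cost is about one line in Section 3.2.1 plus the cross-references. No new test is needed: Table 1 already schedules hematology on Cycle 1 Days 1, 8 and 15 and on Cycle 2 Day 1. The existing conditions on relatedness and disease progression still remove disease-related anemia. The downside is that, rarely, one more event is counted as a DLT.
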